4.6. Study Procedures

Study procedures will follow the Schedule of Assessments (Study Protocol Appendix A, Table 1) and Timing of Sample Collection and Procedures for the Treatment Period (Study Protocol Appendix A, Table 2).

This document is confidential.

5. Endpoints

5.1. Primary Efficacy Endpoint

The primary efficacy endpoint is sputum *P. aeruginosa* density as measured in induced sputum samples at 1 week after end of treatment (Visit 5/Day 17).

5.2. Secondary Efficacy Endpoints

The phage recovery endpoint is based on AP-PA02 levels as measured in induced sputum and venous blood samples at time points specified in the Schedule of Assessments.

5.3. Exploratory Efficacy Endpoints

The exploratory endpoints include the following:

- Anti-Pseudomonas antibiotic sensitivity of *P. aeruginosa* isolates at specified time points during the study;
- Change in *P. aeruginosa* density from Baseline;
- Change from Baseline of in vitro sensitivity of subject *P. aeruginosa* isolates to AP-PA02 and/or individual phage components;
- Change in spirometry from Baseline;
- Change from Baseline levels of induced sputum neutrophil elastase; and
- Change in quality of life as assessed by the following questionnaires:
 - Quality of Life-Bronchiectasis Questionnaire;
 - Leicester Cough Questionnaire; and
 - Saint George's Respiratory Questionnaire.

This document is confidential.

6. Analysis Sets

Subjects who enrolled prior to the first DSMB meeting and received AP-PA02 were given a lower dose (3×10^{11} PFU/day) of AP-PA02. After the first DSMB meeting, a decision was made to increase the dosage of AP-PA02 to 6×10^{11} PFU/day (see [Section 8.5](#)). Unless noted otherwise, summary outputs by treatment groups will exclude subjects who were enrolled on the study prior to the first DSMB meeting that occurred on 01Nov2023 and received AP-PA02.

Subjects who were enrolled on the study prior to the first DSMB meeting but received placebo will be 'pooled' with the subjects who were enrolled after the first DSMB meeting as the 'pooled' placebo group within their respective cohorts.

All subjects will be included in the listings.

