9 STATISTICS

9.1 Analysis Populations

Safety Population: The population for safety analyses will consist of all subjects who receive any AP-PA02 or placebo.

Exploratory Efficacy Population: The population for efficacy (clinical activity) analysis will consist of all subjects who receive any AP-PA02 or placebo with at least 1 Baseline and 1 post-Baseline assessment for the primary efficacy endpoint.

Phage Distribution and Clearance Population: The population for phage distribution analyses will consist of all subjects who receive AP-PA02 and who have at least 1 detectable AP-PA02 concentration measurement in sputum, blood, or urine samples.

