9.2.2 Analysis of Safety

Safety will be assessed by the incidence, severity, grade, and relationship of AEs, including clinically significant changes in vital signs, laboratory data, ECGs, and physical examinations. All safety evaluations will be conducted based on the Safety Population.

Descriptive summaries will be provided by treatment group.

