6.1. Safety Population

The Safety Population will include all subjects who receive any AP-PA02 or placebo. Subjects will be analyzed according to treatment received. The Safety Population will be used for all analyses of safety endpoints and for the presentation of subjects in all subject listings including subject disposition.

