6.2. Exploratory Efficacy Population

The population for efficacy (clinical activity) analysis will consist of all subjects who receive any AP-PA02 or placebo with at least 1 non-zero Baseline measurement and 1 post-Baseline assessment for the primary efficacy endpoint. In addition, subjects with any major protocol violations that could influence the validity of the data for the primary efficacy evaluation will be excluded. All criteria to exclude subjects from the Exploratory Efficacy Population will be made based on a blinded review of the data prior to the unblinding of the study.

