11.3. Spirometry

Spirometry assessments FEV₁, FVC, and FEF₂₅₋₇₅ will be collected locally at the clinical study site. Actual liter values will be recorded. Details regarding spirometry procedures and standards will be included in the Study Manual. Spirometry will be assessed according to the Schedule of Assessments in Table 1 of the Protocol Appendix A and Timing of Sample Collection and Procedures for the Treatment Period in Table 2 of the Protocol Appendix A. Spirometry will be collected prior to sputum induction on non-Treatment Period Visits.

Observed values and mean changes from baseline will be presented for each spirometry parameter using descriptive statistics (i.e., n, mean, standard deviation, median, minimum, and maximum) by treatment group and visit, using the Safety population. If multiple measurements are to be performed at each time

This document is confidential.

point, the highest value will be used for analysis.

A by-subject listing will be provided, including each spirometry parameter, and will be sorted by subject and visit.

A by-subject line plot will be presented by spirometry parameter and cohort. Each cohort will be on a new plot, with all subjects of the same cohort on the same plot. Any unscheduled results will also be part of this plot.

The number and percentage of subjects with PCS values will be summarized by visit/timepoint and for any time post-baseline. Potentially clinically significant values will be identified for FEV₁ (forced expiratory volume) as outlined below.

Table 13.6.1 Potentially Clinically Significant Values for Forced Expiratory Volume Decrease

Parameter	Units	Criteria for PCS Values (Observed values)	
		High	Low
Forced Expiratory Volume	%	NA	70 – 99 60 – <70 50 – <60 <50

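### SAP Section 6's default exclusion of lower-dose AP-PA02 recipients collides with the Safety Population rule, and the SAP does not say which governs the safety tables

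*SAP*

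**What the plan says.** SAP Section 6, ahead of the population definitions, explains that AP-PA02 recipients enrolled before the first DSMB meeting received 3×10^11 PFU/day and that the dose was then raised to 6×10^11 PFU/day. It sets the default "Unless noted otherwise, summary outputs by treatment groups will exclude subjects who were enrolled on the study prior to the first DSMB meeting" and received AP-PA02. Placebo subjects from the same period are kept: "Subjects who were enrolled on the study prior to the first DSMB meeting but received placebo will be" pooled with later placebo subjects within their cohort. All subjects appear in listings.

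The safety rules have no dose or date limit. SAP 6.1 includes everyone treated and adds "The Safety Population will be used for all analyses of safety endpoints". The opening of SAP Section 11 names the same population. Protocol 9.1 says "The population for safety analyses will consist of all subjects who receive any AP-PA02 or placebo", and protocol 9.2.2 says "All safety evaluations will be conducted based on the Safety Population".

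Three other places bear on the point:
- SAP 7.1 presents summaries by treatment group unless specified otherwise.
- SAP 7.6 allows a few unnamed key summaries to be repeated with the early AP-PA02 recipients, as an optional sensitivity analysis.
- SAP Section 13, on changes from the protocol's analysis, is marked not applicable.

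**The concern.** One rule puts a lower-dose recipient in every safety analysis; the other takes the same subject out of every by-treatment-group summary. Both are stated generally, and neither refers to the other.

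Safety is part of the primary objective. If Section 6 governs, the main safety tables describe fewer exposed subjects than were treated, and any safety comparison of the two doses has to be read from listings and plots. If 6.1 governs, lower-dose recipients appear, but the SAP does not say in which column. Two programmers could each follow the SAP and deliver different denominators.

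**Working it through.** **Step 1: which tables are caught.**

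| Output | Layout and population stated | Result |
|---|---|---|
| Laboratory (SAP 11.4) | By treatment group; no table-level exception | Excluded under Section 6; included under 6.1 and the Section 11 opening |
| ECG (11.6) | Shift table by treatment group; threshold counts name no columns | Same; threshold counts are caught through 7.1 |
| Spirometry (11.3, 11.3.1) | Main table "by treatment group and visit, using the Safety population"; FEV1 threshold and FEV1 change summaries name no columns | Direct collision for the main table; the others are caught through 7.1 |
| Vital signs (11.5), compliance (8.6) | Treatment group and Safety Population both named | Direct collision |
| Adverse events (11.1) | By treatment group and overall; a later sentence asks for counts split by dose and study portion | Ambiguous: portion is undefined, and membership of the overall column is not stated |

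**Step 2: does 6.1 count as the exception Section 6 allows for?** SAP 6.2 begins from the same base, "all subjects who receive any AP-PA02 or placebo with at least 1 non-zero Baseline measurement". If such population wording were enough to lift the exclusion, it would lift it for efficacy too and leave Section 6 with little effect. SAP 7.6 also treats including these subjects as a repeat analysis, which implies that the main tables leave them out. On the other side, 6.1 carries an unqualified statement of use for all safety endpoints. The corresponding efficacy statement, at the opening of SAP Section 9, gives way to anything specified elsewhere. The text supports either answer.

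**Step 3: how many subjects.** Neither document gives the number, so this is an illustration.
- Inputs: 24 per cohort at 2:1, so 24 × 2/3 = 16 on AP-PA02 (protocol 9.2.4); first two subjects per cohort are one active and one placebo (SAP 4.4); DSMB reviews at about 10% and/or 50% of enrollment (SAP 2.2).
- Assumptions: the 01Nov2023 meeting fell between those points, the cohorts accrued equally, and excluded subjects were not replaced by extra enrollment.
- Enrolled per cohort: 0.10 × 48 / 2 = 2.4, and 0.50 × 48 / 2 = 12.
- After the sentinel pair, 15 of the remaining 22 in a cohort are active. Expected active enrolled: 1 + 0.4 × 15/22 = 1.27, and 1 + 10 × 15/22 = 7.82.
- Left in the table: about 15 or about 8 of 16.

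**Step 4: what that does to a cohort's table.** For a finding with an assumed true rate of 5%, the chance of at least one occurrence is 1 − 0.95^n:
- n = 16: 0.560
- n = 15: 0.537
- n = 8: 0.337

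With no events seen, the one-sided 95% upper bound is 1 − 0.05^(1/n): 17.1%, 18.1% and 31.2% respectively.

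These are per-cohort figures. No laboratory, vital-sign, ECG or spirometry table is stated to combine the cohorts, so a cross-cohort calculation would describe no committed output.

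**The case against.** The strongest reply is that naming the Safety Population is itself the noted exception. Section 11 opens with it, and 11.3, 11.5 and 8.6 repeat it. This has force: a reader might infer that Section 6 definitely removes these subjects from every safety table, and the documents do not go that far. For spirometry, vital signs and compliance the accurate description is an unresolved conflict. The reply does not settle the matter, because the SAP never says that naming a population overrides Section 6, and 7.6 points the other way. One could also read Section 6 as a rule about which columns are displayed rather than who is in the population. That would ease the contradiction, but the lower-dose results would still be missing from the tables.

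The second reply is that little is lost. Much of this stands:
- The subjects remain in all listings, and the DSMB reviews all available data.
- They remain in the by-subject laboratory plots and the spirometry plots ("Each cohort will be on a new plot, with all subjects of the same cohort on the same plot").
- Disposition and demographics are by cohort and overall, so the full treated count stays visible.
- Antibody titer and physical examination results are only listed in any case.

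The third reply is that the size is unknown and, at a 10% review, trivial. That is correct. The larger figure needs the first meeting to fall at about 50% of enrollment.

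A reader might also infer that the exclusion distorts the percentages. It does not do so by itself, since excluded subjects leave both numerator and denominator. Nor is the dose change in itself a contradiction of the protocol: protocol 3.1.1 allows dose levels to change after DSMB review.

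**Conclusion.** The concern holds as an unresolved conflict of rules that should be settled before the tables are programmed. Section 6 is general in wording, reaches unlabelled tables through 7.1, and conflicts with SAP 6.1, the Section 11 opening and protocol 9.1 and 9.2.2. The optional repeat in 7.6 commits to nothing, and Section 13 declares no departure from the protocol.

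The consequence is lost information and possible inconsistency between tables. Demographics, for example, would keep subjects that the by-treatment-group safety tables drop. The conflict itself rests on the text alone. Its size, about 1 to 8 of 16 AP-PA02 recipients per cohort, rests on the assumed meeting time, equal accrual and no replacement. The fall from 56% to between 54% and 34% also rests on the assumed 5% rate. For adverse events these figures apply only if the ambiguous wording is read as exclusion.

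**What to change.** In SAP Sections 6 and 11:
- State that the exclusion does not apply to safety tables or to the compliance summary in 8.6. Produce these on the full Safety Population by cohort, with subjects grouped by dose received. One workable layout has columns for lower-dose AP-PA02, higher-dose AP-PA02, all AP-PA02 and pooled placebo.
- In 11.1, state who is counted in the overall column, and define or delete the sentence calling for counts by dose and study portion.
- In Section 13, record whatever exclusion remains as a change from the protocol.

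Keeping the doses apart for efficacy may stand. Separately, the daily dose statements in protocol 5.5.3 and in SAP 6 and 8.5 should be reconciled.

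The cost is SAP wording and a few extra table columns, some with small counts. No new data are needed.

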6.1. Safety Population

The Safety Population will include all subjects who receive any AP-PA02 or placebo. Subjects will be analyzed according to treatment received. The Safety Population will be used for all analyses of safety endpoints and for the presentation of subjects in all subject listings including subject disposition.

6.2. Exploratory Efficacy Population

The population for efficacy (clinical activity) analysis will consist of all subjects who receive any AP-PA02 or placebo with at least 1 non-zero Baseline measurement and 1 post-Baseline assessment for the primary efficacy endpoint. In addition, subjects with any major protocol violations that could influence the validity of the data for the primary efficacy evaluation will be excluded. All criteria to exclude subjects from the Exploratory Efficacy Population will be made based on a blinded review of the data prior to the unblinding of the study.

6.3. Phage Distribution and Clearance Population

The population for phage distribution analyses will consist of all subjects who receive AP-PA02 and who have at least 1 detectable AP-PA02 concentration measurement in induced sputum, blood, or urine samples.

This document is confidential.

7. General Aspects for Statistical Analysis

7.1. General Methods

All analyses and summaries will be produced using Statistical Analysis System (SAS®) version 9.4 or higher. All SAS programs used to generate analytical results will be developed and validated according to [REDACTED] and SAS validation procedures. Summaries will be presented by treatment group unless otherwise specified.

Unless otherwise noted, continuous variables will be summarized using the number of non-missing observations (n), arithmetic mean (Mean), standard deviation (SD), median, minimum, and maximum values as summary statistics. The minimum and maximum will be displayed to the precision with which the data were collected. The mean, median, and quartiles will be displayed to one additional decimal place and the SD will be displayed to two additional decimal places, where applicable.

Descriptive statistics for categorical/qualitative data will include frequency counts and percentages. The total number of subjects with a non-missing value for the given variable will be used as the denominator for percent calculations, unless stated otherwise. All percentages will be presented with one decimal, unless otherwise specified. Percentages equal to 100 will be presented as 100, and percentages will not be presented for zero frequencies.

All relevant subject data will be included in listings. All subjects entered into the database will be included in subject data listings. Prior to database lock, the study statistician, data management lead, and medical monitor will review the data entered in the EDC to ensure that the database value falls within reasonable human measurements.

7.2. Key Definitions

7.2.1. Baseline

Unless otherwise specified, baseline is defined as the last non-missing observation prior to the first dose of AP-PA02 or placebo. If time is not collected for an assessment, baseline will be defined as the last non-missing observation on or prior to the first dose date of AP-PA02 or placebo. Assessments conducted on the nominal Baseline visit may not necessarily be flagged as the analysis baseline value.

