5.5.3 Study Drug Administration

The AP-PA02 dose will be administered to each subject as 2 fractionated doses per treatment day. The dosages shown below are estimated (approximate) PFU:

- Each fractionated dose: 1.5×10^{11} PFU;
- Total dose per treatment day: 3×10^{11} PFU; and
- Total dose per 10-day treatment course: 3×10^{12} PFU.

AP-PA02 will be administered in the clinic [REDACTED] during Visit 1/Day 1 (both doses), Visit 2/Day 5 (morning dose only), and Visit 3/Day 10 (morning dose only). Subjects will administer AP-PA02 at home on all other treatment days.

The placebo will be administered in the clinic/at home using the same fractionated dosing schedule and duration as AP-PA02 and [REDACTED]. The placebo will be administered in the clinic during Visit 1/Day 1 (both doses), Visit 2/Day 5 (morning dose only), and Visit 3/Day 10 (morning dose only). Subjects will administer placebo at home on all other treatment days.

On Visit 1/Day 1, clinic staff will administer the first dose of AP-PA02 or placebo. The subject and/or caregiver will administer the second dose of AP-PA02 or placebo with clinic staff observation after the subject has been trained on proper administration. Clinic staff will confirm

the subject/caregiver is comfortable with administering AP-PA02 or placebo during this visit. If the subject is not comfortable administering AP-PA02 or placebo, the subject may visit the clinic for study drug administration until he/she or the caregiver is comfortable with proper study drug administration.

Subjects in Cohort A will receive study treatment (AP-PA02 or placebo) administered as 1 dose distributed over 2 administrations given 6 hours apart on the same day on Day 1 and 10-12 hours apart each day on the remaining days on 10 consecutive days, with 28 days of follow-up after the last study drug dose. Subjects in Cohort B will receive study treatment (AP-PA02 or placebo) administered as 1 dose distributed over 2 administrations given 6 hours apart on the same day on Day 1 and 10-12 hours apart each day on the remaining days for 10 consecutive days plus their current antipseudomonal inhaled antibiotic for 28 days (10 days of study drug treatment plus an additional 18 days). Subjects in Cohort B will also have 28 days of follow-up after the last study drug dose.

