7.5 Urine Phage Titer

Urine samples for phage recovery will be obtained at the visits indicated in the Schedule of Assessments ([Appendix A](#)) using provided collection containers. Date and time will be recorded for each urine sample collection at the designated time points.

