- o. The subject will receive study drug doses for home administration on Visit 1/Day 1 for treatment Days 2 through 4 and on Visit 2/Day 5 for treatment Days 5 (second dose) through 9 and on Visit 3/Day 10 for treatment Day 10 (second dose).
- p. The first 2 subjects in Cohorts A and B will consist of 1 active and 1 placebo subject. Both subjects will be observed for at least 2 days after dosing and if there are no Grade 2 or greater AEs assessed as treatment-related, dosing for the remaining subjects will proceed. Study drug will be administered as 1 fractionated dose of AP-PA02 or placebo (1 dose distributed over 2 administrations given 6 hours apart on the same day on Day 1 and 10-12 hours apart each day on the remaining days) for 10 consecutive days. Subjects will administer AP-PA02 or placebo at home on days they do not visit the clinic. AP-PA02 and placebo will be administered in the clinic during Visit 1/Day 1 (both doses), Visit 2/Day 5 (morning dose only), and Visit 3/Day 10 (morning dose only).
- q. The subject's current antipseudomonal inhaled antibiotic will be administered at Baseline, and for a total of 28 days, 10 days of study treatment and the following 18 days, for subjects in Cohort B only.
- r. Only SAEs will be recorded from Screening until the first dose of AP-PA02 or placebo. After the first dose of AP-PA02 or placebo all AEs will be recorded.

AE = adverse event; CFU = colony-forming units; CT = computerized tomography; d = days; ECG = electrocardiogram; EOS = End of Study; ET = Early Termination; FEF₂₅₋₇₅ = forced expiratory flow between 25% and 75% of the forced vital capacity; FEV₁ = forced expiratory volume; FVC = forced vital capacity; GLI = Global Lung Initiative; HBsAg = hepatitis B surface antigen; HCV = hepatitis C virus; HIV = human immunodeficiency virus; HRCT = high-resolution computerized tomography; LCQ = Leicester Cough Questionnaire; QOL-B = Quality of Life-Bronchiectasis; RNA = ribonucleic acid; SAE = serious adverse event; SpO₂ = oxygen saturation; U = Unscheduled.

Table 2. Timing of Sample Collection and Procedures for the Treatment Period

Visit	Treatment Period								
	1			2		3			
Day	1			5		10			
Time	Prior to first dose	30 minutes after first dose	1 hour after first dose	1 hour after second dose	Prior to first dose	30 minutes after first dose	Prior to first dose	30 minutes after first dose	1 hour after first dose
Induced sputum sample (required)				*	*				*
Sputum culture					X				X

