7.2.2. Study Day

The day of first dose of treatment administration is defined as study Day 1. Subsequent days are numbered consecutively (Day 2, Day 3, etc.). Prior to the day of first dose of treatment administration, study days are numbered sequentially with negative values (i.e., Day -1, Day -2, etc.). There is no Day 0.

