9.2.4. Change from Baseline levels of induced sputum neutrophil elastase

Biomarkers, including induced sputum neutrophil elastase, will be collected at all study visits from Baseline through EOS and tested by the central laboratory. Change from Baseline through EOS will be summarized using descriptive statistics at each scheduled time point and will be presented by treatment group. Subjects with a missing value at Baseline or post Baseline will not be included in the summary from change from Baseline.

9.2.5. Change in quality of life as assessed by the Quality of Life-Bronchiectasis (QOL-B) Questionnaire

The QOL-B Questionnaire is a self-administered PRO measure designed specifically for subjects with bronchiectasis¹, and will be self-administered at Baseline, Visit 4/Day 11, and Visit 6/Day 24. This PRO contains 37 items on 8 scales: Respiratory Symptoms, Physical, Role, Emotional and Social Functioning, Vitality, Health Perceptions, and Treatment Burden. Each of the 37 items are scored from 1-4, and each of the 8 scale scores are standardized on a 0-100 point scale with higher scores indicating fewer symptoms or better functioning and health related QOL. A total score is not calculated.

SAS programming code for calculating scores for the 8 scales is provided in [Appendix 15.1](#). The scaled scores for each of the 8 scales and absolute change from Baseline will be summarized by visit using summary statistics for continuous variables by treatment group.

9.2.6. Change in quality of life as assessed by the Leicester Cough Questionnaire (LCQ)

The LCQ is a 19-item self-completed QOL measure of chronic cough with is responsive to change², and will be administered at Baseline, Visit 4/Day 11, and Visit 6/Day 24. The LCQ contains 19 items which assess three domains: physical (8 items), psychological (7 items), and social (4 items). Subjects will respond to each item using a 7-point Likert response scale.

Questions 1, 2, 3, 9, 10, 11, 14, and 15 comprise the physical domain; questions 4, 5, 6, 12, 13, 16, 17 comprise the psychological domain; and questions 7, 8, 18, 19 comprise the social domain. For each domain, scores are calculated by determining the mean for that domain (sum of scores from items in the domain / number of items in domain; range 1-7). Total LCQ scores are calculated by summing the domain scores (range 3-21).

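### If no clock time is collected for sputum neutrophil elastase, the SAP's date-only baseline rule selects the Day 1 sample scheduled after both doses (minor; exploratory endpoint)

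*SAP*

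**What the plan says.** SAP 7.2.1 gives a general rule and a fallback. Under the general rule, "baseline is defined as the last non-missing observation prior to the first dose of AP-PA02 or placebo". The fallback reads: "If time is not collected for an assessment, baseline will be defined as the last non-missing observation on or prior to the first dose date". The section adds: "Assessments conducted on the nominal Baseline visit may not necessarily be flagged as the analysis baseline value". The value from the nominal Baseline Visit is therefore not protected.

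SAP 7.2.2 fixes the date in question: "The day of first dose of treatment administration is defined as study Day 1".

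Protocol Appendix A, Table 1 schedules biomarkers at the Baseline Visit (Day -7 to -1), at Visit 1/Day 1 and at every later visit, but not at Screening. In Table 2 the only Day 1 mark in the biomarker row is at "1 hour after second dose". Protocol 5.5.3 has the two Day 1 administrations "given 6 hours apart on the same day on Day 1".

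SAP 9.2.4 analyzes elastase against this baseline: "Change from Baseline through EOS will be summarized using descriptive statistics at each scheduled time point". It gives no baseline definition of its own.

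**The concern.** The general rule is strictly pre-dose. The fallback replaces the comparison of times with a comparison of dates, and it lets in anything measured on the dosing day. That is harmless for an assessment whose Day 1 measurement is pre-dose. It is not harmless for an assessment whose only Day 1 measurement follows treatment, and elastase is such an assessment.

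If the fallback applied, the baseline would come after two inhalations of AP-PA02 in one arm and two of placebo in the other. Any movement in elastase during those first hours would be taken out of every later change from baseline. If the arms moved differently on Day 1, the descriptive comparison between them would shift by that difference.

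**Working it through.** No sample size, power or alpha figure is involved. The check applies the two baseline rules to the schedule.

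**Step 1: read Table 2 by column.** There are nine timed columns. Day 1 has four: before the first dose, 30 minutes after it, 1 hour after it, and 1 hour after the second dose. Day 5 has two: before the first dose and 30 minutes after it. Day 10 has three: before the first dose, 30 minutes after it and 1 hour after it.

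| Row | Day 1 marks | Pre-dose mark on Day 1? |
|---|---|---|
| Biomarkers | 1 h after second dose | No |
| Induced sputum, sputum phage titer, blood phage titer | 1 h after second dose | No |
| Sputum culture | none | – |
| Clinical laboratory | before first dose | Yes |
| 12-lead ECG | before first dose; 1 h after first dose | Yes |
| Spirometry | before first dose; 1 h after second dose | Yes |
| Vital signs and SpO₂ | before first dose; 30 min after first dose; 1 h after second dose | Yes |

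The biomarker marks fall in columns 4, 5 and 9. The other rows support this alignment: the laboratory row and the first ECG mark fall in the Day 1 pre-dose column, where they would be expected.

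**Step 2: place the sample in time.** The interval between the Day 1 administrations is 6 h and the sample is 1 h after the second, so it is nominally 6 + 1 = 7 h after first exposure.

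**Step 3: apply each rule to the elastase schedule.**
- Time collected: the last observation before the first dose is the Baseline Visit sample.
- Time not collected: the last observation dated on or before Day 1 is the Visit 1 sample, taken after both doses.

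**Step 4: look for a rule that overrides this.** SAP 9.2.4 has none. SAP 7.4 takes the earliest value when a visit has repeats, but Visit 1 has only one biomarker sample, and it is post-dose.

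**Step 5: consequence for change from baseline.** Let B be the Baseline Visit value, D the Day 1 value and Y a later value.
- Change at Day 1 = D − D = 0.
- Reported later change = Y − D = (Y − B) − (D − B).

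Each later change is therefore offset by whatever change was already present at the Day 1 sample. The documents give no figure for D − B. With assumed values and a true change Y − B = −1.0 (arbitrary units):

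| Assumed D − B | Reported change |
|---|---|
| 0 | −1.0 |
| −0.25 | −0.75 |
| −0.5 | −0.5 |
| −1.0 | 0.0 |

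The table shows only the mechanism. If elastase has not moved by the Day 1 sample, nothing shifts.

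**Step 6: primary endpoint.** Neither table schedules a sputum culture on Day 1, so the baseline for *P. aeruginosa* density cannot be a Day 1 post-dose value by this route.

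**The case against.** The strongest objection is that the trigger is not shown. The fallback applies only where time is not collected, and no document says this of sputum biomarker samples. Protocol 7.5 states for urine that "Date and time will be recorded for each urine sample collection at the designated time points", and nothing equivalent appears for sputum, but silence does not show that times are absent. Urine phage titer has no row in Table 2, so the sentence may only supply timing that the table lacks. Biomarkers also come from the same required induced sputum block as the phage titer, and phage kinetics belongs to the primary objective, so recorded sampling times are plausible. The case report form and laboratory manual would settle this, and they are not among the documents. This objection stands, and it makes the point conditional.

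A second objection is intent. SAP 9.2.4 evidently treats visits after Baseline as post-baseline, and output review could notice a Day 1 change of zero in every subject. That is fair, but it relies on someone overruling the written rule.

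A reader might infer more than the documents support:
- *That vital signs, spirometry and ECG are equally exposed.* The fallback wording does not exclude their later Day 1 readings. However, each has a Day 1 pre-dose reading, and the SAP reports vital signs, and potentially clinically significant spirometry and ECG values, by time point. Their scheduled time points must therefore be identifiable. SAP 7.4 also points to the earliest reading for vital signs and ECG, although spirometry has its own highest-value rule.
- *That it affects each subject whose Day 1 record lacks a time.* The wording concerns time not being collected for an assessment, which is most naturally a feature of data collection. Handling of a single missing time is a separate matter that the SAP does not address.
- *That the elastase comparison is biased in a known direction.* This needs an acute Day 1 effect that differs between arms, and the documents give no evidence for or against one.

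**Conclusion.** The point holds as a conditional fault in a stated rule. For elastase without a clock time, SAP 7.2.1 as written selects a sample nominally 7 h after the first dose over a genuine pre-dose sample, and no other text corrects it. Whether the condition is met is unknown. If times are collected, the general rule already gives the right baseline.

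The reach is limited to one exploratory endpoint that is summarized descriptively. The size and direction of any distortion cannot be determined from the documents. The conclusion rests on the column reading of Table 2 and on the fallback being applied literally. Severity is minor.

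**What to change.** Add to SAP 7.2.1: *A record whose scheduled time point in Protocol Appendix A, Table 2 is after dosing is never eligible as baseline. Where time is not collected for an assessment, the nominal time point decides whether a Day 1 record is pre-dose.*

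Add to SAP 9.2.4: *The baseline for neutrophil elastase is the Baseline Visit sample.*

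The cost is a few sentences in the SAP, with no new data. Results do not change if times are collected. If they are not, a subject without a Baseline Visit sample has no elastase baseline, since Table 1 schedules no biomarker sample at Screening. SAP 9.2.4 already leaves subjects with a missing baseline out of the change summary. The 7.2.1 wording also settles the Day 1 readings for vital signs, spirometry and ECG.
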